8 GENERAL DESIGN ISSUES

The study design consists of three parallel arms: placebo and two final doses of SRX246 (120 mg BID and 160 mg BID). Thirty-six patients will be randomized into each study arm. Since we have only given SRX246 to generally healthy subjects thus far, and since some HD patients may be frailer population, we have elected to initiate treatment at 80 mg BID; to increase the dose of drug to 120 mg BID after two weeks in those patients who have tolerated the starting dose; and to increase the dose of drug again after 2 additional weeks in those patients who are taking 160 mg BID. Subjects in the placebo group will take capsules that will be identical in appearance to those containing SRX246. Thus, patients and study staff will both be blind to treatment, and twice as many Subjects will receive active agent as placebo. The placebo group will be used for comparison with each active drug group.

Subjects who are unable to increase their dose of drug can remain in the study at the highest dose they can tolerate, and Subjects who find the drug intolerable can reduce the dose of drug (to 80 mg BID of SRX246 or placebo, but no lower without dropping out of the study). The goal is to study the behavioral scales in as many people as possible because we feel that this will be important to the clinical research community.

At the end of the trial, data from all Subjects who were given placebo will be combined, and two pairwise tests will be performed (120 mg vs placebo, 160 mg vs placebo--see below).

It may be necessary to screen as many as 150 candidates to enroll 108 Subjects. Up to 20 NeuroNEXT sites may participate in the study, with each site's goal to enroll about 5-6 Subjects within the first 18 months of the trial.

8.1 Outcomes

8.1.1 Primary Outcome: Tolerability

The primary endpoint will be tolerability, defined as the proportion (percentage) of completers. Each treatment group will be compared to the control group, and the statistical test of equivalence of tolerability will involve two pairwise tests (120mg vs placebo, 160mg vs placebo).

8.1.3 Exploratory Aim: Activity

The exploratory aim is to examine several measures of irritability and other problem behaviors, and clinical assessments for activity signal. The following measures will be compared to each other in order to examine relative effect sizes. The endpoint will be rate of change (slope) over 12 weeks.

Unified Huntington Disease Rating Scale (UHDRS)
Clinical Global Impression (Severity, CGI-S and Improvement, CGI-I)
Aberrant Behavior Checklist (ABC), irritability subscale

Cohen-Mansfield Aggression Inventory (CMAI)
Problem Behaviors Assessment – short form (PBA-s)
Irritability Scale (IS)
HD QoL
Caregiver Burden Questionnaire

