- Perform clinical assessment for suicidal ideation with the CSSRS.
- Conduct UHDRS assessment (Huntington Study Group 1999).
- Total Functional Capacity (TFC) score must be between 5-13, inclusive.
 - TFC is <7, an assessment of capacity to consent will be required.
- Evidence of irritability must be met, i.e., a score of at least 2 or greater on the severity measure of either the UHDRS Irritability question (30b) or the Aggression question (Disruptive or Aggressive Behavior, 31b).
- Assess the Subject using the Clinical Global Impression – Severity of Illness (CGI-S).
- Administer the Problem Behaviors Assessment short form (PBA-s) to the Subject and Study Partner, together.

- Administer the Aberrant Behavior Checklist (ABC), irritability subscale to the Study Partner.
- Administer the Cohen-Mansfield Agitation Inventory (CMAI) to the Study Partner.
- Administer the HD Irritability Scale (IS) to the Subject and Study Partner, separately.
- Administer the HD QoL to the Subject and Study Partner, together.
- Administer the Caregiver Burden Questionnaire to the Study Partner.

After the Baseline (BL) visit activities have been completed and the Subject is deemed eligible to participate in the study, the site Coordinator will enroll the Subject into the study by accessing the online data capture tool for enrollment. Once the system confirms requirements for eligibility have been met, a random Enrollment ID number corresponding to study drug will be generated and assigned to the Subject. Once the Subject has been randomized, the site will complete the following additional activities:

- Administer first dose of study drug (80mg BID SRX246 dose or Placebo).
- Perform orthostatic vital sign measurements: blood pressure (systolic and diastolic) and heart rate (beats/minute) approximately 1-2 hours after first dose (estimated time to Cmax).
- Inquire about any immediate side effects (e.g., nausea, dizziness, GI discomfort).
- Dispense study drug supplies (80mg BID SRX246 dose or Placebo) for the next 2 weeks, and complete drug accountability/ management log.
- Instruct Subject and Study Partner about correct administration of study drug, remind the Subject to begin taking capsules twice daily (in the morning and in the evening), beginning the morning of the next day.
- Instruct Subject and Study Partner to bring unused study drug to each study visit, and to immediately report any AEs to the Investigator or Coordinator.

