6.5 Visit 02 (Week 6) Day 42±5

The following procedures will be performed during this visit (this visit may take about 3 hours):

- Assess the Subject for possible AEs and Concomitant Medication use.
- Review amount of study drug returned and assess compliance.
- Review the use of the eDiary and encourage the Subject and Study Partner to make and upload entries two times per day.
- Perform orthostatic vital sign measurements: blood pressure (systolic and diastolic) and heart rate (beats/minute).
- Record the Subject's weight (kg) and obtain body temperature (°C).
- Perform a resting 12-Lead EKG.
- Collect blood samples for routine hematology/serum chemistry, and for a serum pregnancy test for women of childbearing potential (refer to Section 6.13.5 for required tests).
- If two tubes not collected at Baseline Visit (Day 0), collect blood samples for CAGn genotyping and/or DNA storage (refer to University of Rochester Medical Center Lab Manual for sample handling and processing requirements).
- Collect urine for routine urinalysis (refer to Section 6.13.5 for required tests).
- Perform clinical assessment for suicidal ideation with the CSSRS (Since Last Visit).
- Conduct UHDRS assessment (Huntington Study Group 1999).
- Total Functional Capacity (TFC) score must be between 5-13, inclusive.
 - TFC is <7, an assessment of capacity to consent will be required.
- Assess the Subject using the Clinical Global Impression – Improvement (CGI-I).
- Administer the Problem Behaviors Assessment short form (PBA-s) to the Subject and Study Partner, together.
- Administer the Aberrant Behavior Checklist (ABC), irritability subscale to the Study Partner.
- Administer the Cohen-Mansfield Agitation Inventory (CMAI) to the Study Partner.
- Administer the HD Irritability Scale (IS) to the Subject and Study Partner, separately.
- Administer the HD QoL to the Subject and Study Partner, together.

- Administer the Caregiver Burden Questionnaire to the Study Partner.
- Dispense study drug and instruct the Subject and Study Partner about correct administration of study drug (i.e., either remaining at 120 mg BID SRX246 or Placebo, change in dose to 160 mg BID SRX246 or Placebo, or possible dose reduction based on intolerance).
- Instruct Subject and Study Partner to bring unused study drug to each study visit, and to immediately report any AEs to the Investigator or Coordinator.

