6.11 Premature Withdrawal (PW)

Subjects have the right to withdraw from the study at any time without prejudice. The site Investigator may withdraw study drug from a Subject in the study in the event of intercurrent illness, adverse events, other reasons concerning the health or well-being of the Subject, or in the case of lack of cooperation, non-compliance, protocol violation or other administrative reasons. Premature withdrawal will be implemented in the case of emergency disclosure of drug treatment (i.e., unblinding).

A Subject may withdraw or be withdrawn from the study for the following reasons:

Administrative

1. Withdrawal of consent
2. Request of [Sponsor or Principal Investigator]

3. Request of primary care physician
4. Non-compliance
5. Failure to meet entry criteria
6. Pregnancy
7. Protocol deviation
8. Subject deemed lost to follow up/failure to return
9. Early termination of study
10. Other

Adverse Event

1. Worsening of the disease under study
2. Worsening of pre-existing disease (other than disease under study)
3. Intercurrent illness
4. Death
5. Major/clinically significant alteration in laboratory values after beginning study drug
6. Other adverse event

In the event of premature withdrawal from the study, every effort should be made to obtain an in-person final visit, which should include the same procedures as Visit 05 (Week 12). This can be performed whether or not the withdrawal is determined at a regularly scheduled study visit or at an unscheduled visit. Visit T2 should still be performed 7±5 days after the final in-person visit.

Should a scheduled in-person visit be impossible, conduct as many of the verbal assessments as possible, with special emphasis on obtaining information on possible AEs, and arrange for return of study drug.

Reasons for withdrawal of the Subject prior to completion of the study must be stated in the CRF and in the site source documentation for all study Subjects who were enrolled in the study. The CCC and the IMM must be informed within 24 hours of all study Subjects who are withdrawn due to an adverse event.

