The Clinical Global Impression Scale (CGI), Caregiver Burden Assessment (CBA), and HD Quality of Life Scale (HD QoL) will measure the global impact of HD on the quality of life and general well-being of patients and their caregivers. The instruments are intended to supplement the measures of irritability and can be predicted to respond similarly, as they encompass the consequences of neuropsychiatric symptoms. Each has been used previously in

studies of HD patients. Additionally, the CGI has been used as a primary outcome measure in many conditions, including neurodegenerative and neuropsychiatric disorders, because it assesses the rater's impression of whether there is a response to a treatment. This study provides an opportunity to relate these global measures to performance to the irritability measures and the TFC.

The Clinical Global Impression (CGI) scales are frequently used as a primary or secondary outcome measure in psychiatric and cognitive disorders. This assessment must be completed by the site Investigator.

The Clinical Global Impression - Severity scale (CGI-S) is a 7-point scale that requires the clinician to rate the severity of the patient's illness at the time of assessment, relative to the clinician's past experience with patients who have the same diagnosis. Considering total clinical experience, a patient is assessed on severity of illness at the time of rating: 1, normal, not at all ill; 2, borderline ill; 3, mildly ill; 4, moderately ill; 5, markedly ill; 6, severely ill; or 7, extremely ill.

The Clinical Global Impression - Improvement scale (CGI-I) is a 7 point scale that requires the clinician to assess how much the patient's illness has improved or worsened relative to a baseline state at the beginning of the intervention: 1, very much improved; 2, much improved; 3, minimally improved; 4, no change; 5, minimally worse; 6, much worse; or 7, very much worse.

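### CGI-S (Baseline only) and CGI-I (weeks 6 and 12 only) are listed for a 12-week slope analysis that their rating schedules do not support, and the AIC rule for choosing scales ignores direction

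*Protocol*

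**What the plan says.** Protocol 8.1.3 introduces its list of activity measures with two statements: "The following measures will be compared to each other in order to examine relative effect sizes" and "The endpoint will be rate of change (slope) over 12 weeks". The list contains "Clinical Global Impression (Severity, CGI-S and Improvement, CGI-I").

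Protocol 8.2 (Exploratory Aim) gives the model. It has one intercept shared by all arms and described as the level at baseline, a placebo slope beta, slope differences gamma (120 mg) and delta (160 mg), a random intercept and random slope for each patient, and residual error. A full and a reduced model (without gamma and delta) are fitted to every irritability and clinical measure in turn. The measure or few measures with the largest AIC difference become candidates for later efficacy trials.

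The rating schedule is in the visit sections:

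- Protocol 6.2 (Baseline) asks for the "Severity of Illness (CGI-S") form.
- Protocol 6.5 (week 6) and 6.8 (week 12) ask for the "Improvement (CGI-I") form and not the severity form.
- Visits 01, 03 and 04 (6.3, 6.6, 6.7) ask for neither.
- The withdrawal visit (6.11) is one "which should include the same procedures as Visit 05 (Week 12"), so it adds CGI-I but no CGI-S.

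Protocol 6.13.6.5 defines CGI-I as a rating "relative to a baseline state at the beginning of the intervention", with mid-scale categories "3, minimally improved; 4, no change; 5, minimally worse". SAP 8.1 names the CGI without saying which form, when or by what model, and keeps these analyses out of the final study report.

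**The concern.** A slope needs at least two ratings over time. A common-baseline slope model also needs a rating at baseline if its intercept is to mean what the protocol says. CGI-S fails the first condition and CGI-I the second. A further gap lies in the selection rule: AIC difference measures how well a scale separates the arms, not whether the separation favours SRX246.

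Learning which scales to carry into later trials is a stated purpose of the study (Protocol 2.1.2 and 2.1.5). As written, one listed analysis is impossible, one uses a model that its data do not identify, and a scale could be named a candidate with no stated check that patients on drug improved. How to handle each of these would then be decided after the data are seen.

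**Working it through.** The documents give no numerical result for this analysis, so there is no figure to reproduce. The check sets the Protocol 8.2 model against the visit schedule.

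**CGI-S, t = 0 only.** The fixed-effect columns are 1, t, t·g120 and t·g160. At t = 0 the last three are all zero, so the design has rank 1 of 4. The full and reduced likelihoods are equal. The AIC difference (reduced minus full) is LRT - 2 × 2 = 0 - 4 = -4, whatever the drug does. Because LRT cannot be negative, -4 is the lowest possible value.

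**CGI-I, t = 6 and 12: covariance.** The model has four covariance parameters: intercept variance g11, covariance g12, slope variance g22 and residual variance s². Two visits supply three equations:

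- Var(week 6) = g11 + 12·g12 + 36·g22 + s²
- Var(week 12) = g11 + 24·g12 + 144·g22 + s²
- Cov(6, 12) = g11 + 18·g12 + 72·g22

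The rank is 3 of 4. For scales rated at weeks 0, 6 and 12 there are six equations and the rank is 4 of 4. The fixed-effect design for CGI-I has rank 4 of 4, so beta, gamma and delta can be computed.

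**CGI-I: what the fixed slopes mean.** I fitted the four fixed-effect columns by generalised least squares to assumed arm means, with equal arms and an assumed within-patient correlation of 0 to 0.7 (compound symmetry, which simplifies the protocol's covariance). Both active arms share the same means, and 4 on the scale is no change.

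| Assumed effect | Ratings at weeks | Intercept | Slope difference per week | Placebo drift over 12 weeks (12 × beta) |
|---|---|---|---|---|
| Step: placebo 4, 4; active 3, 3 | 6, 12 | 3.33 | -0.100 to -0.068 | 0.80 to 0.55 |
| Same step, all arms 4 at week 0 | 0, 6, 12 | 3.89 | -0.100 to -0.088 | 0.13 to 0.03 |
| Linear: placebo 4, 4; active 3.5, 3 | 6, 12 | 4.00 | -0.083 | 0 |
| Same linear effect, all arms 4 at week 0 | 0, 6, 12 | 4.00 | -0.083 | 0 |

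Under the step effect at correlation 0, the true differences of -1 at both visits are fitted as 6 × (-0.10) = -0.60 and 12 × (-0.10) = -1.20. A flat placebo arm appears to worsen by 12 × 0.0667 = 0.80 points. Under the linear effect nothing is distorted.

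**Direction.** AIC difference = LRT - 4 on two unrestricted parameters, so reflecting the data leaves it unchanged. In one simulated data set it was -0.23 before and after reflection. Over 30 simulated trials (36 per arm; visits at weeks 0, 6 and 12; assumed SDs of 5 for the intercept, 0.3 per week for the slope and 3 for the residual) the mean AIC difference was 8.5 (SE 1.1) for a slope difference of -0.3 per week in both active arms, and 8.3 (SE 1.2) for +0.3.

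**The case against.** **CGI may not belong in the ranking.** Protocol 1.3 puts CGI under a separate exploratory objective, and SAP 8.1 keeps that split. Protocol 8.2 writes the model for an irritability score and describes the comparison measures as motor, cognitive and functional. The CGI entry in 8.1.3 might also be meant as one instrument with a baseline form and a follow-up form. This has some force. However, 8.1.3 names both forms under the slope endpoint, and 8.2 applies the models to clinical as well as irritability measures. Inclusion is the more natural reading, and nothing in either document excludes CGI.

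**The CGI-I distortion depends on the assumed shape.** This stands. A reader might infer that the CGI-I slope is always biased or that CGI-I cannot be analysed. Neither follows. The protocol assumes linear change, and under a linear effect the CGI-I fit agrees with a scale rated at weeks 0, 6 and 12. A step effect is also turned into a slope on those other scales; at correlation 0 the slope difference is -0.10 for both. The larger contrasts concern the intercept and placebo slope, which the AIC comparison does not test. Visit windows and withdrawal visits could add some information on the covariance if actual dates are used, but never a week-0 rating.

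**Direction will be seen anyway.** Gamma and delta are signed, 8.2 says that slope differences will be examined, and the AIC step is a screen for candidates rather than a claim of benefit. Sign-invariance is a property of any such test, so the simulation only illustrates it. What remains is narrower: the written rule for naming candidates does not use the signs.

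**Conclusion.** The point holds at low severity.

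- **CGI-S:** the listed slope analysis cannot be done. This rests only on the visit schedule. A reader might infer that CGI-S could distort the choice of scales; it could not, because its AIC difference sits at the floor of -4.
- **CGI-I:** the stated model is not identified at the two nominal visits (3 of 4 covariance parameters), and its intercept refers to a week-0 rating that does not exist. Fixed slopes can be computed. They mislead only if the effect is not linear from week 0: for the assumed step effect, an intercept of 3.33 instead of 4 and a placebo drift of 0.55 to 0.80 points; for a linear effect, none.
- **Direction:** a scale on which drug worsens patients would rank the same as one showing equal benefit under the rule as written. The documents do not support the stronger inference that a harmful signal would go unnoticed, since the signed estimates come from the same fit.

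The CGI conclusions about the ranking assume that CGI is among the clinical measures in Protocol 8.2. The consequences are confined to the exploratory choice of scales. The tolerability Go/No-Go does not use these measures, and SAP 8.1 places them outside the final study report.

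**What to change.** 1. Remove CGI-S from the slope list in Protocol 8.1.3 and use it as a baseline descriptor or covariate.
2. Analyse CGI-I as a level outcome at weeks 6 and 12, for example with an ordinal model adjusted for baseline CGI-S, and keep it out of the AIC ranking.
3. For the remaining scales, state beforehand which direction is benefit. Scales differ: a higher Total Functional Capacity score is better, while a higher CGI-I rating is worse. Report gamma and delta with confidence intervals, and require them to favour drug before a scale is named a candidate on its AIC difference, saying for which dose.

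SAP 8.1 is the natural place for this text, since it gives no model or selection rule now. The cost is wording and minor programming; no new visits or data are needed.

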8.2 Sample Size and Accrual

Primary Aim: Analysis and Sample Size. The study design consists of three parallel arms: placebo and two final doses of SRX246 (120mgBID, 160mgBID). The primary endpoint will be tolerability, defined as the proportion (percentage) of completers. Each treatment group will be compared to the control group, and the statistical test of tolerability will involve two pairwise tests (120 mg vs placebo, 160 mg vs placebo). Our immediate focus will be on a single test using an alpha-correction for multiple comparisons.

The Go/No Go decision for further consideration of SRX246 will be based on testing tolerance among the placebo (P) and treatment (T) groups using a single-tailed test. Because equality of tolerance is consistent with the Go decision, there is perhaps a temptation to under-power a study using the traditional test of the null hypothesis of equal group population proportions. Setting a low sample size will make it difficult to reject the null and perhaps provide an unfair or unrealistic test of equal tolerability. As an alternative, we propose a test of non-inferiority (Blackwelder 1982) that powers for the rejection of the null hypothesis that the population proportion difference is greater than or equal to a margin value, δ . Suppose π_T is the proportion of completers for the T group and π_P is the same for the P group. The null hypothesis and alternative hypothesis of non-inferiority are respectively, $H_0: \pi_P - \pi_T \geq \delta$, $H_A: \pi_P - \pi_T < \delta$, so that under H_A , $\pi_T > \pi_P - \delta$ (the T completer proportion is greater than the P proportion adjusting for the margin). Equivalence of tolerability within the margin is consistent with the rejection of the null hypothesis and will constitute a Go decision for further consideration of SRX246, perhaps in a Phase IIb study to detect signs of activity. Conversely, failure to reject the null hypothesis will result in a No Go decision.

The advantage of the non-inferiority approach is that sample size planning can be based on the power to reject the null hypothesis, which is consistent with traditional approaches. If the sample size is large, H_0 can be evaluated using an asymptotic single-tailed test, with z-value

$$z = \frac{\hat{\pi}_P - \hat{\pi}_T - \delta}{\sqrt{\frac{\hat{\pi}_P(1-\hat{\pi}_P)}{n_P} + \frac{\hat{\pi}_T(1-\hat{\pi}_T)}{n_T}}}$$

where n_P is the sample size for the P group, and total sample size is $N = 3n_P$.

The above equation indicates that a power analysis for planned sample size requires candidate values for π_P , π_T and δ , for fixed type 1 error rate (α) and type 2 error rate (β). Following the practice of the Huntington Study Group (HSG 1998; 2003; 2004; 2009), the margin was set at $\delta = 0.50$ for all analyses, though a follow-up margin sensitivity analysis was performed (see below). A difference of 50% between P and T is considered acceptable because of the paucity of effective treatments for HD (HSG 1998). For the remaining parameters, plausible values were based on published literature for randomized clinical trials (RCTs) in HD.

Table 4 below shows completer information for P and T groups of six HD RCTs employing various drugs.

Table 4. Tolerability information from HD clinical trials.

Study	Drug	N	Completer Percentage		
			Placebo	Treatment	Difference
HSG (2009)	Tetrabenazine	84	97%	91%	6%
Kieburtz (2010)	Latrepirdine	91	82%	87%	5%
HSG (1998)	OPC-14117	64	94%	81% ^a	13%
HSG (2003)	Riluzole	63	91%	87% ^a	4%
HSG (2004)	Minocycline	60	96%	78% ^a	18%
Squitieri (2013)	Pridopidine	353	86%	86% ^a	0%

[figure not shown]
Note. ^aPercentage is the minimum among multiple treatment arms.

Placebo completion rate ranged from 82%-97% and the group difference ranged from 0%-18%. In light of the information in Table 4, sample size was computed for

$\pi_P = 0.80, 0.85, 0.90, 0.95$ and $\pi_P - \pi_T = 0.01, 0.02, \dots, 0.19, 0.20$. It should be noted that the minimum $\pi_P = 0.80$ is less than any placebo value in Table 4, and the maximum $\pi_P - \pi_T = 0.20$ is greater than any difference in Table 4, so these values constitute reasonable bounds for selecting required sample size. The non-inferiority test is single-tailed, and the type I error rates of $\alpha = .05 / 2 = .025$, and $\alpha = .10 / 2 = .05$ were used to allow for two comparisons (each dose level versus placebo), with power set at 80% ($\beta = 0.20$).

The results of the power analysis are shown in Figure 4 below. The Figure shows the single-arm sample size (n_P) as a function of the P group proportion (π_P), and the group proportion difference ($\pi_P - \pi_T$) paneled by α -level. As discussed, the combination of $\pi_P - \pi_T = 0.20$ and $\pi_P = 0.80$ appear to be reasonable bounds for sample size selection. In the left-hand panel, the upper red line shows that conducting two tests each at $\alpha = .025$ and 80% power requires approximately 35 participants per group for the smallest proposed control proportion ($\pi_P = 0.80$) and the largest proportion difference ($\pi_P - \pi_T = 0.20$). Therefore, we propose a total sample size of $N = 3n_P = 105$.

[figure not shown]
Figure 4. Sample size for the placebo group as a function of effect size, placebo proportion, and alpha-level (80% power).

Further Sample Size Considerations. The power analysis suggests that a total sample size of $2n_p = 70$ will be used for each comparison of completer proportions (120mg vs placebo, 160mg vs placebo). The margin used to derive this sample size, $\delta = 0.50$, allows the possibility of a relatively small proportion of completers in the T group. For example, if $\pi_p = 0.90$, H_0 will be rejected if $\pi_p > 0.40$, meaning there could be a minority of completers. In order to assess the sensitivity of the sample size to a change in margin value, we examined the power of the z-test for the observed values in Table 4 with $n_p = n_T = 35$ fixed for all calculations, and $\alpha = 0.025$ to allow for two comparisons. Figure 5 shows power as a function of the Table 4 P group proportions, group proportion differences, and various margin values. The vertical dashed line indicates the mean group difference of 0.08 (mean P proportion is 0.91), and 80% power is indicated by a horizontal dashed line. Using the mean Table 4 values as a reference, the middle panel indicates that with the selected sample size the margin can be decreased to 0.30 and still provide 80% power to reject H_0 (the point defined by the intersection of the dashed lines). Assuming the mean values of Table 4, the 0.30 margin allows for rejection of H_0 for $\pi_T > 0.61$. If the proportions of the proposed study are equal to the mean values of Table 4, then the statistical power will be high enough to reject H_0 for a margin as low as 0.30 with a majority of completers in the T group. We also note that the left-most panel of Figure 5 shows that an even lower margin (e.g., $\delta = 0.20$) will provide adequate power if the P and T proportions are relatively close to 1 and approximately equal (close to no difference).

Figure 5. Power for $n = 35$ per group as a function of Table 4 placebo group proportion, group proportion difference (placebo minus treatment), and margin value.

The dashed horizontal line indicates the conventional 80% power value and the vertical dashed line indicates the average Table 4 group difference.

An additional consideration is that using the asymptotic test with our estimated sample size might not be optimal. The asymptotic test can be inaccurate with smaller sample sizes, especially when π_P (or π_T) is close to 1, as is anticipated in the proposed study (cf Table 4) (Fagerland 2011). Computer-intensive exact methods can have better performance under these conditions (Santner 2007). The exact method discussed by Wang (2010) will be used for the proposed analysis of tolerability and safety (the latter is discussed below). Wang's method appears to have superior performance to other approaches, and software is readily available (Wang 2013).

Secondary Aim: Safety. The secondary aim of the analysis is safety, with the endpoint defined as the proportion of participants who experience an adverse event (AE). A non-inferiority analysis for safety will be performed, similar to that discussed for tolerability. Primary focus will be on the comparison of 160mg vs placebo. H_0 for non-inferiority will be evaluated using the methods previously described with the same margin of difference, $\delta = 0.50$.

Consistent with the recent JAMA Guide to Statistics and Medicine (Detry 2014) the analysis will be performed consistent with the intent-to-treat principle, meaning an attempt will be made to analyze all enrolled patients. Missing data methods, such as imputation, might be used to handle dropout (note this is not an issue for the tolerability analysis as the proportion of completers is the endpoint).

Exploratory Aim: Activity of Measures. The exploratory aim is to examine several measures of irritability and other problem behaviors and clinical assessment for activity signal. Measures will be compared to each other and also compared to clinical assessments in order to examine relative

effect sizes. The endpoint will be rate of change (slope) over 12 weeks. Linear mixed models (LMMs) (Verbeke 2000) will be used to examine slope differences among the placebo and treatment groups. LMMs are appropriate for the analysis because they account for dependency due to repeated measures and can be estimated with maximum likelihood (ML) procedures.

Consistent with the intent-to-treat principle, ML estimation can accommodate missing data under the assumption that the missing data mechanism is ignorable (Little 1987).

Suppose Y_{ij} is the irritability score for the i th patient ($i = 1, \dots, N$) at the j th week ($j = 1, \dots, n_i$), and t_{ij} denotes time in weeks. Assuming linear change over time, the LMM can be written as the following,

$$Y_{ij} = \alpha + \beta t_{ij} + \gamma t_{ij}g_{120i} + \delta t_{ij}g_{160i} + (a_i + b_i t_{ij} + \epsilon_{ij})$$

where g_{120i} is a dummy variable for the 120mg group membership (1 = in the group, 0 = otherwise), and g_{160i} is a dummy variable for the 160mg group. In the equation, α is the intercept (baseline level) that is common among groups due to random assignment; β is the slope for the placebo group; γ is the 120mg vs placebo slope difference; and δ is the 160mg vs placebo slope difference. The terms a_i and b_i are the random effects (random intercepts and slopes, respectively), and ϵ_{ij} is random error. We make the typical assumptions, $[a_i \ b_i]^T \sim \mathcal{N}(\mathbf{0}, G)$, $\epsilon_{ij} \sim \mathcal{N}(0, \sigma^2 I_i)$, and $[a_i \ b_i]^T \perp \epsilon_{ij}$.

An evaluation of the null hypothesis that the slopes are equal among the groups can be performed with the likelihood ratio test (LRT). The LRT is based on a comparison of the full model above and a reduced model omitting $\gamma t_{ij}g_{120i} + \delta t_{ij}g_{160i}$. Alternatively, a global effect size can be computed as the difference of Akaike's information criterion (AIC) for the full and reduced model (Burnham 2002). The statistical strategy is to estimate the full and reduced model for each irritability and clinical variable separately. Then the difference in AIC for each variable (full vs reduced model) can be used to assess relative strength of effect in discriminating among the groups. Because larger AIC differences indicate larger effect sizes (i.e., greater discrimination), the variable with the largest AIC difference (or the top few variables) will be a candidate for further study in clinical trials of efficacy. AIC differences of the irritability variables relative to the clinical variables will provide a context for judging the effect size of the former compared to general motor, cognitive, and functional variables in HD. The difference in AIC has been found to be a useful method of screening candidate variables for efficacy in HD research (Leoni 2013, Paulsen 2013).

